# 1.0 Eligibility

Older adults with overweight or obesity will be recruited by flyers posted around the University of Illinois at Chicago (UIC) campus and on social media. Subject eligibility will be assessed and determined by [name] Ph.D., R.D. Screening will be conducted in-person at the Human Nutrition Research Unit (HNRU) located in the Applied Health Sciences Building ([name]).

## 1.1 Inclusion criteria:

- Age between 50 to 70 years old
- BMI between 25 and 50 kg/m^2
- Pre-diabetic (fasting glucose: 100-125 mg/dl or HBA1c 5.7%-6.4%)
- Sedentary or lightly active 
- Are post menopausal (absence of menstural cycle for 1 year)

# 1.2 Exclusion criteria:

- Diabetic (fasting glucose: >126 mg/dl or HBA1c >6.5%)
- Have a history of eating disorders (anorexia, bulimia, or binge eating disorder)
- Have uncontrolled hypertension, any other cardiovascular disease, or history of aneurysm
- History of alcohol dependance (score >20 from Alcohol and Health Questionnaire)
- Are not weight stable for 3 months prior to the beginning of study (weight gain or loss > 4 kg)
- Are not able to keep a food diary or activity log for 7 consecutive days during screening
- Are taking drugs that influence study outcomes (weight loss, glucose-lowering medications)
- Are premenopausal, perimenopausal or have an irregular menstrual cycle (menses that does not appear every 27-32 days)
- Mobility disability (unable to exercise for 40-60 minutes 3-5 days/week)
- Diagnosed comorbidities including systemic diseases (Parkinson's cirrhosis, renal disease or systemic rheumatic conditions), cancer, or cognitive impairment
- Are night shift workers
- Are smokers

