# 2.0 Subject enrollment

Independently living subjects from the Chicago area will be recruited by flyers posted around the University of Illinois at Chicago (UIC) campus. The flyer will also be posted to social media outlets including: Instagram, Facebook, and Twitter. All study procedures will be conducted at the Human Nutrition Research Unit (HNRU) located in the Applied Health Sciences Building ([name]).

Each subject will attend 1 screening visit. During **Visit 1** subjects will be screened by the Study Manager, [name] Ph.D., RD, via questionnaire, which will assess eligibility based on the requirements listed above. The following parameters will also be assessed: body weight and height (for BMI), a blood draw (for fasting glucose/diabetic status). Alcohol and Health Screening questionnaire will be administered to determine history of alcohol dependence (questionnaire is attached to submission). The Study Manager will also distribute a 7-day food record and provide detailed instructions on how to complete the records. Follow-up with participants virtually will be scheduled 10 days after the first screening. The food record will be assessed for adequacy (to evaluate each participant's motivation to participate in the study) and fasting blood glucose (via glucometer) will be taken. Consent will be obtained prior to the administration of the screening questionnaire by a member of the study team (key research personnel identified in Appendix P).

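### The prediabetes inclusion range and the diabetes exclusion do not meet, so a person at exactly 126 mg/dl or 6.5% is eligible when the other marker is in range

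*Combined protocol and SAP*

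**What the plan says.** Section 1.1 (Inclusion criteria) of the combined protocol and SAP asks for "Pre-diabetic (fasting glucose: 100-125 mg/dl or HBA1c 5.7%-6.4" per cent. The two markers are joined by *or*, so either one in range satisfies the criterion.

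Section 1.2 (Exclusion criteria) removes people described as "Diabetic (fasting glucose: >126 mg/dl or HBA1c >6.5" per cent. Both comparisons are strictly greater than, and the markers are again joined by *or*, so either one alone is enough to exclude.

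The only other criterion that bears on glycaemia is the drug exclusion in Section 1.2, "Are taking drugs that influence study outcomes (weight loss, glucose-lowering medications", which sets no glucose or HbA1c limit.

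Section 2.0 (Subject enrollment) says how status is assessed. At Visit 1 there is "a blood draw (for fasting glucose/diabetic status", and at a follow-up 10 days later "fasting blood glucose (via glucometer) will be taken". It gives no rule for boundary values, for markers that disagree, or for which glucose reading decides.

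**The concern.** An inclusion range and the exclusion above it should share a boundary. Here the range stops at 125 mg/dl and 6.4%, and exclusion starts only above 126 mg/dl and 6.5%. The values 126 and 6.5% fall in neither list.

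Had inclusion required both markers in range, the gap would do no harm, because anyone at a boundary value would fail inclusion. Since one marker suffices, the other can sit in the gap and the person still qualifies.

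At stake is who belongs to the trial population. Section 3.0 plans 20 people in four non-randomized arms of 5, so one such person is 1/5 = 20% of an arm, and there is no randomization to balance the arms on glycaemic status. Two screeners could also decide the same case differently, one going by the label prediabetic and the other by the printed numbers.

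**Working it through.** The plan gives no figure to reproduce here; the check is of the logic of the two lists.

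**Inputs**
- Include (Section 1.1) if 100 ≤ glucose ≤ 125 **or** 5.7 ≤ HbA1c ≤ 6.4.
- Exclude (Section 1.2) if glucose > 126 **or** HbA1c > 6.5.
- Eligible on glycaemia = included and not excluded.

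**Boundary cases taken one at a time**

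| Glucose (mg/dl) | HbA1c (%) | Meets inclusion? | Excluded? | Eligible as written? |
|---|---|---|---|---|
| 126 | 5.7 to 6.4 | yes, on HbA1c | no | **yes** |
| 100 to 125 | 6.5 | yes, on glucose | no | **yes** |
| 126 | 6.5 | no | no | no |
| 126 | below 5.7 | no | no | no |
| below 100 | 6.5 | no | no | no |
| 110 | 6.6 | yes, on glucose | yes, on HbA1c | no |

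The first two rows are the problem. The next three show that a boundary value alone does not admit anyone. The last shows that the exclusion already takes precedence once it is triggered.

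**Grid count.** The rules were evaluated on whole mg/dl from 80 to 140 and HbA1c in steps of 0.1% from 5.0 to 7.1.
- Eligible combinations on glucose: 26 values (100 to 125) × 16 HbA1c values (5.0 to 6.5) = 416.
- Eligible combinations on HbA1c: 8 values (5.7 to 6.4) × 47 glucose values (80 to 126) = 376.
- Counted in both: 26 × 8 = 208.
- Total eligible: 416 + 376 − 208 = 584.
- Of these, at glucose 126: 8 (HbA1c 5.7 to 6.4). At HbA1c 6.5: 26 (glucose 100 to 125). Together 8 + 26 = 34.

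These are combinations of values, not people. They show where the gap lies, not how often it would be met.

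**After the change.** With exclusion at glucose above 125 or HbA1c above 6.4, none of the 34 remains eligible and the other 584 − 34 = 550 are untouched.

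**Rounding.** The plan does not state reporting precision. If results are given in whole mg/dl and tenths of a per cent, the gap is one value per marker. Unrounded results between 125 and 126 mg/dl, or between 6.4 and 6.5%, would fall in it too.

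**The case against.** The strongest reply is that this is a wording slip at a single reportable value per marker, and that a screener would probably exclude such a person anyway. Nothing in the documents shows that 126 rather than 125, or 6.5% rather than 6.4%, would change any result. That stands, and it is why the point is minor. It does not remove the point, because the written rule does not require the exclusion.

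A second reply is that the route through glucose 126 needs an HbA1c result at screening, and Section 2.0 does not name HbA1c among the screening tests. If HbA1c were not measured, a person at 126 would fail inclusion. That is fair. But both eligibility lists use HbA1c, and the blood draw is said to cover diabetic status, so it is reasonable to assume that it is measured.

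A third is that a greater-than-or-equal sign was lost when the PDF was read. This cannot be ruled out, but such a sign survives in the equipment-spacing rule of the exercise protocol, and nothing supports a loss here.

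Several stronger readings are tempting and are not supported:
- *Anyone at 126 or 6.5% is admitted.* No: the other marker must be in its prediabetic range.
- *The* or *lets clearly diabetic values through.* No: anything above 126 or above 6.5% is excluded whatever the other marker shows, so no override sentence is missing.
- *Boundary people would undertake fasting with exercise.* Under Section 3.0 only two of the four arms combine them. One arm fasts without exercise and the control arm does neither.
- *The chance of enrolling such a person can be stated.* If a share p of otherwise eligible people sat at a boundary, the chance of at least one among 20 would be 1 − (1 − p)^20, which is 18% for p = 1% and 56% for p = 4%. The documents neither give nor bound p, so these figures only illustrate the formula and nothing here rests on them.

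**Conclusion.** The point holds. As written, a person at exactly 126 mg/dl with HbA1c 5.7 to 6.4%, or at exactly 6.5% with glucose 100 to 125 mg/dl, is outside the plan's own prediabetic range on one marker and is still eligible. No other criterion or screening rule closes the gap.

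Severity is minor. The conclusion assumes that the printed inequality signs are the intended text and that both markers are available at screening. How many people are affected is unknown and probably few. The 20% weight of one person uses the arm size of 5 in the Section 3.0 text; the intervention table in that section prints 50 per group, where one person would be 1/50 = 2%. The gap in the criteria is the same either way.

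**What to change.** Reconcile Sections 1.1 and 1.2. The smallest change is to begin the exclusion immediately above the plan's own inclusion limits: any fasting glucose above 125 mg/dl or any HbA1c above 6.4%. Worded in that way, it also covers unrounded values, and no value above the prediabetic range escapes exclusion.

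If the sponsor means to admit 126 mg/dl and 6.5%, the inclusion range should be extended to say so. Requiring both markers in range would also close the gap, but it would turn away people with one marker in range and the other below it, which is a larger change to the population.

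The cost is two thresholds in one line. The effect on recruitment should be small, since only the boundary values are affected, but the documents give no frequency to confirm it.

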# 2.0 Subject enrollment

Independently living subjects from the Chicago area will be recruited by flyers posted around the University of Illinois at Chicago (UIC) campus. The flyer will also be posted to social media outlets including: Instagram, Facebook, and Twitter. All study procedures will be conducted at the Human Nutrition Research Unit (HNRU) located in the Applied Health Sciences Building ([name]).

Each subject will attend 1 screening visit. During **Visit 1** subjects will be screened by the Study Manager, [name] Ph.D., RD, via questionnaire, which will assess eligibility based on the requirements listed above. The following parameters will also be assessed: body weight and height (for BMI), a blood draw (for fasting glucose/diabetic status). Alcohol and Health Screening questionnaire will be administered to determine history of alcohol dependence (questionnaire is attached to submission). The Study Manager will also distribute a 7-day food record and provide detailed instructions on how to complete the records. Follow-up with participants virtually will be scheduled 10 days after the first screening. The food record will be assessed for adequacy (to evaluate each participant's motivation to participate in the study) and fasting blood glucose (via glucometer) will be taken. Consent will be obtained prior to the administration of the screening questionnaire by a member of the study team (key research personnel identified in Appendix P).

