## 3.0 Study design and procedures

A 10-week non-randomized, controlled, parallel-arm trial, divided into a 2-week baseline and an 8-week intervention will be implemented. Older subjects with overweight or obesity (n = 20) will be assigned to 1

*Time restricted feeding with physical activity for weight management Version 4, 07/19/21*  of 4 groups: (1) TRE (n = 5) ad libitum food intake from 12 pm to 8 pm, fasting (with zero-calorie beverages) from 8 pm to 12 pm daily, (2) TRE + EN (n = 5), TRE diet as stated in group 1 plus 3-4 days of 40-60 minutes of endurance exercise per week; or 3) TRE + RT (n = 5), TRE diet as stated in group 1 plus 3-4 days of 40-60 minutes of resistance training per week 4) control (n = 5), ad libitum food intake daily with no meal timing restrictions. In-person study activities will be carried out at the Human Nutrition Research Unit (HNRU) located in the Applied Health Sciences Building ([name]) or at Coalition Strength and Conditioning ([name]).

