# Diet protocol

TRE group and combination groups (8-h eating window): During the weight loss period, the TRE groups will be instructed to eat ad libitum from 12-8pm daily, and fast from 8-12 pm (16-h fast). During the 8-h eating window, there will be no restrictions on types or quantities of foods consumed. Moreover, participants will not be required to monitor caloric intake during this ad libitum feeding period. During the fasting period, participants will be encouraged to drink plenty of water and will be permitted to consume energy-free drinks, such as black tea, coffee, and diet sodas (limit 2 diet sodas/d, since these beverages may increase sugar craving ). TRE participants will meet with the dietitian every week (by phone or zoom) throughout the weight loss period to review their diet adherence. Subjects will also be taught how to make healthy food choices that conform to ADA nutrition guidelines.

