**Control group protocol:** Controls will be instructed to maintain their weight throughout the trial, and not to change eating or physical activity habits. Controls will visit the research center at the same frequency as the treatment groups (for outcome measurements) to control for investigator-interaction bias between groups. Controls will be offered free weight loss diet counseling (4 sessions) at the conclusion of the study by [name]., RD.

**Weekly check-in:** Weekly check-in calls will be done with all participants regardless of group at a prespecified time weekly via either zoom or telephone based on the participant preference. This appointment time will remain the same throughout the 10 weeks. During this call the study coordinator will address possible issues with compliance, difficulty with the intervention, and complete the adverse events questionnaire verbally. Time stamped weigh in photos and adherence logs will also be requested at this appointment. Further, dietary counseling to support the participant will be included in each call by a registered dietitian ([name], RD). Diet counseling will not include weight loss counseling, but general lifestyle improvement so as can be also given to the control group for weight maintenance. All counseling will be based off of recommendations from the Academy of Nutrition and Dietetics, The American Heart Association, and Healthy People 2020. Topics will include:

- Increasing fruit and vegetable intake
- Reading food labels
- Water intake
- Lean protein
- Healthy fats
- Whole grains
- A balanced plate Choices for eating out

*Time restricted feeding with physical activity for weight management Version 4, 07/19/21*  **Subject compensation.** No compensation or parking reimbursement is offered for trial completion. Participants will be able to have access to all data received from the study. In addition, controls will receive 4 free diet counseling sessions at the conclusion of the study.

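### No eligibility rule screens out people who already eat within about 8 hours a day, so for some TRE-arm participants the diet component can be little or no change

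*Combined protocol and SAP*

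**What the plan says.** The Diet protocol (section 3.0) defines the intervention: "the TRE groups will be instructed to eat ad libitum from 12-8pm daily, and fast from 8-12 pm (16-h fast"). It sets no limit on what or how much is eaten in the window. Controls have "ad libitum food intake daily with no meal timing restrictions" (section 3.0), and the control-group paragraph under Exercise protocol adds: "Controls will be instructed to maintain their weight throughout the trial, and not to change eating or physical activity habits".

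Sections 1.1 and 1.2 list 5 inclusion and 12 exclusion criteria. The one exclusion tied to daily timing is "Are night shift workers". The one tied to the food diary is "Are not able to keep a food diary or activity log for 7 consecutive days during screening", which concerns completing it rather than what it shows.

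Section 2.0 describes screening "via questionnaire, which will assess eligibility based on the requirements listed above". On the 7-day record it says: "The food record will be assessed for adequacy (to evaluate each participant's motivation to participate in the study").

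The Study activities table schedules another food record and a diet-adherence item in the first baseline week. Section 5.0 specifies a linear mixed model with time, diet and time × diet effects, and names no term for the baseline eating window.

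**The concern.** A shorter eating window is essentially the whole planned diet difference between TRE and control, because general dietary counselling goes to every group. That difference exists only if participants normally eat over a longer period. A weight-stable person who skips breakfast and finishes dinner by 8 pm meets every listed criterion. Assigned to a TRE arm, that person would look fully adherent while changing almost nothing.

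The plan already guards against the same problem for exercise: section 1.1 admits only people who are inactive or lightly active, so training is a real change. The diet component, shared by three of the four arms, has no such safeguard. At stake is a smaller TRE-versus-control difference, and a null result that could not be told apart from the absence of a real change in eating pattern.

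**Working it through.** The documents give no effect size, SD, significance level, power or sample-size derivation, so there is no plan figure to reproduce. The check is a reading of the criteria followed by simple arithmetic.

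**1. Can such a person be enrolled?** The nearest criteria are these:
- Night-shift work: does not concern the eating window.
- Eating-disorder history: does not cover someone who simply eats late.
- Weight stability, "Are not weight stable for 3 months prior to the beginning of study (weight gain or loss > 4 kg"): a habitual short-window eater at stable weight passes.
- Keeping a diary for 7 days: passes if the diary is complete.
- Screening questionnaire: limited to the listed criteria.

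Nothing later catches the person. No assignment or analysis rule uses the baseline food record or adherence item.

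**2. Effect on the change contrast.** Let δ be the TRE effect on change for someone whose window really shortens. Assume it is zero for someone already eating at about 12–8 pm. Let c be the change shared by both arms, and p the fraction of such people in the TRE arm.

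- Mean change, TRE arm: c + (1 − p)δ
- Mean change, control arm: c, whatever its own share of short-window eaters
- Difference (the time × diet contrast): (1 − p)δ

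To keep the same power, N per arm rises by 1/(1 − p)². This ignores the extra spread that a mixed arm adds, so it is slightly low.

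| TRE arm size (source) | Short-window eaters | p | Effect kept | N multiplier |
|---|---|---|---|---|
| 5 (section 3.0 text) | 1 | 1/5 = 20% | 0.80 | 1/0.80² = 1.56 |
| 5 | 2 | 2/5 = 40% | 0.60 | 1/0.60² = 2.78 |
| 50 (interventions table) | 1 | 1/50 = 2% | 0.98 | 1/0.98² = 1.04 |

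If the diet factor pools the three TRE arms, which section 5.0 leaves open, one person among 15 is 1/15 = 6.7%.

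**3. How likely is it?** The prevalence is not in the documents. The values below are assumptions, with 5 per arm. The chance of at least one such person among n is 1 − (1 − p)ⁿ.

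| Assumed p | At least 1 of 5 | At least 1 of 15 in TRE arms | Effect kept | N multiplier |
|---|---|---|---|---|
| 5% | 23% | 54% | 0.95 | 1.11 |
| 10% | 41% | 79% | 0.90 | 1.23 |
| 20% | 67% | 97% | 0.80 | 1.56 |
| 30% | 83% | 99.5% | 0.70 | 2.04 |

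**4. Power, for scale only.** This uses a two-sided 5% t-test with noncentrality d(1 − p)√(n/2), where d is an assumed standardized effect. For n = 5 and d = 1.5, power is 55%, 47%, 39% and 31% at p = 0, 10%, 20% and 30%. For n = 50 and d = 0.5, it is 70%, 61%, 51% and 41%.

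**5. Combination arms.** If exercise adds an effect E, the contrast with control is E + (1 − p)δ. The share lost is pδ/(E + δ), which is below p when both effects point the same way.

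**6. Uneven spread.** With additive effects, TRE + EN minus TRE alone equals E + (p_TRE − p_EN)δ. One short-window eater in a TRE arm of 5 and none in TRE + EN would add 0.2δ to the apparent exercise effect.

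**The case against.** The strongest objection is that the frequency is unknown: every prevalence above is assumed, and the true loss could be near zero. That stands. So does the point that such enrolment dilutes the effect of TRE as assigned without invalidating any stated analysis.

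Four stronger readings are tempting, and the documents do not support them.

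- *Controls already on TRE also shrink the effect.* For change over time they do not. A control who keeps existing habits contributes about zero change, like any other stable control. The harm is a blurred comparator and blurred comparisons of levels.
- *The intervention is void for any short-window eater.* The window is fixed at noon to 8 pm, so someone eating early in the day must still shift hours. In TRE + EN and TRE + RT the supervised exercise is still new.
- *One such person always costs 20%.* That holds only in a TRE arm of 5. It is 2% in an arm of 50, and about nothing in the control arm.
- *Recruitment attracts people who already fast.* The documents mention flyers and social media but do not show the flyer's content. Uneven spread can be argued only from the non-randomized assignment, for which no method is given.

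One could also measure the window and describe or adjust for it, without excluding anyone. That is cheaper in screen failures, but it cannot restore a diet change that never took place, and adjustment has little to work with at 5 per arm.

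**Conclusion.** The gap is real and of moderate importance. Followed exactly, the plan can enrol people for whom the diet component is little or no change, and nothing later identifies them. The expected TRE-versus-control difference in change falls to about (1 − p) of its full size, where p refers to the TRE arm only. This assumes no diet effect in people whose window does not change, which is fully true only if they already eat at about 12–8 pm. Because p is unknown, the loss can be stated only per person, and it depends on which of the two conflicting arm sizes is correct. The point supports a change to screening. It does not show that the trial is invalid.

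**What to change.** 1. In section 2.0, have the 7-day screening record capture the clock time of first and last intake each day. The documents do not say whether the present form does. Use the record for eligibility as well as adequacy.
2. In section 1.2, add an exclusion for a habitual eating window not clearly longer than 8 hours, or for current or recent intermittent fasting or time-restricted eating. The sponsor should set the cut-off and the look-back period. A window of 10 hours or less on most recorded days is one example, not a derived figure; it would also turn away people with 9–10-hour windows, for whom 8 hours is still a reduction.
3. Report the baseline eating window by group, so that any uneven spread is visible.
4. Reconcile the 5 per group in the section 3.0 text with the 50 per group in the interventions table.

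The cost is two time fields on a form already collected, one added criterion and some extra screen failures. No new visit is needed, since the record is already reviewed at the follow-up 10 days after the first screening.
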